**Table 3**

*Overview of Study Measures*

Measure	Baseline Survey	28-Day Monitoring Period	Follow-Up Survey
Demographic information, medical/mental health history	X		
BPI, PCS, PSEQ, HADS, PSQI	X		X
Daily self-monitoring survey (via app), daily self-monitoring survey completion time		X	
TLFB, acceptability survey, validity of responses			X

## **Data Analysis Plan**

### ***Effect Size Estimation***

The major goal of this Stage I pilot RCT is to estimate the effect size of the primary outcome variables (Rounsville et al., 2001). This will be done by using the means and variances of the CM and Co groups on the primary outcome variables. This estimated effect-size will then be used to perform power analyses and sample size calculations to be used in the design of a larger clinical trial.

### ***Sample Size Justification***

As this is a Stage I pilot study and no preliminary data are available, a power analysis is not provided. Sample size was determined by anticipating a medium effect size (.05), 80% power, alpha level=.05 (Cohen, 1988). For two-sided *t*-tests, 32 participants/group are needed. This would allow us to detect an effect size of  $d=.711$ , which falls between medium,  $d=.05$  and large,  $d=.8$  effect sizes. Recruitment of 80 subjects with 80% retention was expected to achieve this effect size.

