### ***Baseline Visit Call***

During the 5-10-minute Zoom or telephone call RAs will review the following with all study participants: verify study eligibility; complete randomization to CM or Co groups; set up the DynamiCare Rewards app on the participant's smartphone; and remind them that they would receive daily text message reminders to complete the daily survey. RAs also will encourage participants to set an alarm or some other reminder of their own. In addition, for participants randomized to the CM condition, RAs will review CM procedures, including their debit card,

and they explain that they will receive an initial draw and reward for setting up the app.

Participants will also be offered handouts summarizing the information discussed in the call.

**Randomization.** Participants who complete the baseline visit call and are verified as eligible for the study will be randomly assigned to either the CM ( $n = 46$ ) or Co ( $n = 35$ ) condition. To determine group assignment, study staff will use an Excel spreadsheet with randomization groups determined by a random numbers app and prepared by [name] in advance of study launch. Each row with a randomization group will be numbered sequentially and correspond to a participant's study ID number. Study staff will not see the randomization group until they indicate that the participant is enrolled in the study and ready to be randomized. No stratification variables are proposed for this Stage I pilot study (see Rounsville et al., 2001).

**DynamiCare Rewards App.** DynamiCare is an iOS and Android app which fully automates CM methodology. The app will be customized for the present study, incorporating the daily self-monitoring survey and incentives plan. After randomization, all participants will be added to the DynamiCare Analytics portal and received an email with the link to download the app on their smartphone. Once participants successfully downloaded the app, RAs instructed them in the use of the app.

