**All Participants.** Day 1 of the daily surveys will start the day after the app is downloaded and the account is set up. Participants will be encouraged to complete the daily survey and pick a time of day to set a personal reminder. They will receive a text reminder around noon each day from a study smartphone. The daily survey data will automatically be uploaded to the DynamiCare HIPAA-compliant server. Participants' DynamiCare Rewards accounts will be manually archived after they completed the 28-day survey period.

**CM Group.** Participants randomized to the CM group will have the chance to receive incentives for complying with the target behavior (completing daily self-monitoring surveys within a 12-hour window (8am-8pm) over a 28-day period. Daily self-monitoring surveys and the delivery of incentives were completed using the DynamiCare Rewards app. The escalating variable-ratio reinforcement schedule used for the study was modeled after the fishbowl method developed by Petry et al. (2005a) and Olmstead and Petry (2009).

Behavioral incentives will be managed remotely via the app to facilitate extrinsic motivation for participant follow-through with self-monitoring. Participants will be able to draw from a fishbowl via the app to determine their monetary prize. Participants will be given an initial draw for downloading the app and completing training during the baseline call, which will be set to \$8. When they meet the target behavior, participants will be awarded additional draws through the app. The number of draws they earn will increase by one for every day they completed the survey. The maximum number of draws they could earn over the course of the 28-day period was 236. Failure to complete a daily self-monitoring survey, however, resulted in a reset to baseline (1 draw per completed daily self-monitoring survey) and 3 consecutive completed daily self-monitoring surveys will be required for a participant to return to the highest level achieved prior to reset. Additional engagement with the app will not result in additional monetary reinforcement.

***Incentives.*** Specifically, reward amounts ranged from \$0-50 in value. Half (50%) of incentives will be “good job” and not associated with a monetary reward. The app will be connected to reloadable debit cards (The Next Step debit card, provided by True Link Financial, Inc.), which will be activated and mailed to CM participants within one to two weeks of their baseline call.

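### The stated basis for the sample size (a medium effect at 80% power) does not give 32 per group: 32 corresponds to d = 0.711, and a medium effect would need 64 per group

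*Combined protocol and SAP*

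**What the plan says.** All the main statements are in one paragraph, Data Analysis Plan, Sample Size Justification.

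- It opens by saying that no power analysis is given, because this is a Stage I pilot without preliminary data.
- It then gives a basis for the size: "Sample size was determined by anticipating a medium effect size (.05), 80% power, alpha level=.05 (Cohen, 1988").
- For two-sided t-tests it concludes that "32 participants/group are needed".
- The next sentence begins "This would allow us to detect an effect size of" and gives d = .711, which it places between a medium effect (printed .05) and a large one (.8).
- It ends: "Recruitment of 80 subjects with 80% retention was expected to achieve this effect size".

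Three other sections bear on this. Effect Size Estimation says: "The major goal of this Stage I pilot RCT is to estimate the effect size of the primary outcome variables". Outcome Measures compares both primary outcomes (number of surveys completed, longest unbroken run) between groups by independent t-tests. The randomization paragraph under Baseline Visit Call says that eligible participants "will be randomly assigned to either the CM" arm (n = 46) or the control arm (n = 35), whereas the sample-size paragraph assumes equal groups.

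**The concern.** If a medium effect at 80% power had fixed the sample size, the effect detectable with 80% power at that size would be the medium effect. By the paragraph's own account it is larger. The two sentences therefore give two incompatible bases for the same number.

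At stake is how the result is read. Someone relying on the first sentence would believe that the trial has 80% power for a medium effect and could take a null result as evidence against one. The plan also passes the effect-size estimate on to the design of a larger trial, so that team needs a correct account of what this sample can show.

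**Working it through.** **Inputs from Sample Size Justification.** Two-sided t-test, alpha 0.05, power 80%, 32 per group, detectable d = 0.711, 80 recruited, 80% retained. **From the randomization paragraph:** 46 and 35. **Inference:** the documents never print 0.5. Reading .05 as 0.5 follows from the label medium, from its place beside .8 for large, and from the statement that .711 lies between the two.

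**Method.** For arms n1 and n2, the t statistic is noncentral t with n1 + n2 − 2 degrees of freedom and noncentrality d × √(n1·n2/(n1 + n2)). Power is the probability that it exceeds the two-sided 5% critical value in absolute size.

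**1. The plan's own figure.** With 32/32, √(32·32/64) = 4, there are 62 degrees of freedom and the critical value is 1.999.
- d = 0.711: noncentrality 4 × 0.711 = 2.844, power 79.9%.
- Solving for n at d = 0.711 and 80% power gives 32.04 per group. Solving for d at 32 per group gives 0.7115.
- Retention: 80 × 0.80 = 64 = 2 × 32.

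So 32, .711, 80 recruited and 80% retention all agree with each other.

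**2. The stated basis, a medium effect.**
- d = 0.5 with 32/32: noncentrality 4 × 0.5 = 2.0, power 50.4%.
- n per group for d = 0.5 at 80% power: 63.8, so 64. The normal approximation agrees closely: 2 × (1.960 + 0.842)²/0.5² = 15.70/0.25 = 62.8, so 63.
- At the plan's retention, 2 × 64 = 128 analysed would mean 128/0.80 = 160 recruited.

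**3. Could another reading give 32?**
- d = .05 taken literally: 15.70/0.0025 is about 6,280 per group, and power with 32/32 is about 5%.
- One-sided test at alpha 0.05, d = 0.5: 50.15, so 51 per group; power with 32/32 is 63%. The paragraph specifies two-sided tests in any case.
- A large effect, d = 0.8: 25.5, so 26 per group; power with 32/32 is 88.3%.

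Of these, only d of about 0.711 gives 32.

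**4. The allocation stated elsewhere.** The plan does not define the analysis set. The primary outcomes come from the app ("The daily survey data will automatically be uploaded to the DynamiCare HIPAA-compliant server"), so loss at the follow-up survey need not remove anyone from them. The range is:

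| Analysed | √(n1·n2/(n1+n2)) | Power at d = 0.5 | d at 80% power |
|---|---|---|---|
| 32/32 | 4.00 | 50.4% | 0.71 |
| 46/35, all 81 | 4.46 | 59.6% | 0.64 |
| about 37/28, if 80% retention applies (assumption) | 3.99 | 50.2% | 0.71 |

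None comes near 80% for a medium effect.

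**5. Precision for the estimation goal.** SE(d) = √((n1 + n2)/(n1·n2) + d²/(2(n1 + n2))). At d = 0.5:
- 32/32: √(0.0625 + 0.00195) = 0.254; 95% half-width 1.96 × 0.254 = 0.50.
- 46/35: √(0.0503 + 0.00154) = 0.228; 95% half-width 1.96 × 0.228 = 0.45.

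**The case against.** The strongest reply is that this is a pilot which disclaims a power analysis and makes estimation its main goal. It also prints .711 and says that this exceeds a medium effect, so the reader is told what the design can detect. On that view one clause and two misplaced decimals are at fault, and nothing in the conduct of the trial changes.

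Much of this stands, and it limits the harm. It does not remove the contradiction. Having disclaimed a power analysis, the paragraph goes on to give an effect size, power, alpha, group size and detectable effect, and these must agree. Both primary hypotheses are still tested.

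A second reply is that 46 and 35 may be realised enrolment, which does not belong in a planning justification. The documents do not say so; the counts appear as the planned assignment. The figures based on them are therefore conditional, and the contradiction does not depend on them.

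A third is that the primary outcomes are counts bounded by 28 days, so t-test power to one decimal is too exact. That is fair: about 50% and about 60% are as precise as the text should be.

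**Conclusion.** The concern holds. The claim that a medium effect at 80% power determined the size is wrong. With 32 per group the two-sided 5% t-test has 80% power at d of about 0.71 (and more for larger effects), and about 50% at d = 0.5. A medium effect needs 64 per group, a factor of two.

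Reading .05 as 0.5 is an inference, but neither value gives 32. The power figures assume roughly normal outcomes and equal groups; under the 46/35 allocation, power at d = 0.5 is about 50% to 60%, depending on who is analysed. The point should be fixed. It does not invalidate the trial, since the detectable effect is disclosed and estimation is the main aim.

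**What to change.** Change the Sample Size Justification as follows.

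1. Correct both effect sizes printed as .05 to 0.5. The .05 given for alpha is right and stays.
2. Replace the statement that a medium effect at 80% power determined the size with the actual basis for 32 per group, which the sponsor must supply. If the basis was 80 recruited, 80% retained and a detectable d of 0.711, saying so would be enough. Reword the opening disclaimer to match, since a power calculation follows it.
3. State the consequence, for example: *With 32 analysed per group, the two-sided 0.05 t-test has 80% power for d = 0.71 and about 50% power for a medium effect (d = 0.5).*
4. If the 46/35 allocation is kept and all 81 are analysed for the app-recorded outcomes, state d = 0.64 and about 60% instead. If 80% retention is taken to apply to those outcomes (about 37/28), say so; the figures then stay at 0.71 and about 50%.

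The cost is a few sentences and a less favourable stated power for a medium effect. No outcome, test, allocation or enrolment target changes.

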### ***Incentives for Self-Reporting of Prescription Opioid Use***

Finan et al. (2017) recently investigated the variability of Rx opioid use and associations with pain and related factors in patients with sickle cell disease who received incentives for completing a daily electronic diary ( $N=45$ ). They found that greater pain and pain catastrophizing were associated with greater use of short-acting opioids, and negative affect was associated with greater use of long-acting opioids. Adherence to self-monitoring was problematic in their study, with one-fourth (25%) of the sample excluded for having <25% of self-reports, with an additional 25% of the remaining sample having missing data. These findings highlight the value of remote self-monitoring of pain severity, related factors, and Rx opioid use for providing information that aids effective opioid prescribing. Results also demonstrate the need to better understand how to improve adherence to self-monitoring of these variables.

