### ***Informed Consent***

Individuals who meet eligibility criteria, indicate that they want to participate in the study, and provide their contact information will be emailed a link to the REDCap study informed consent form within one business day of completing the screener. The VCU IRB granted a waiver for signed informed consent. This consent form describes the purpose of the study, involvement in the study (e.g., randomization to two study groups, completion of daily surveys for 28 days, baseline and follow-up assessments, compensation, etc.); the voluntary nature of the study; limits of confidentiality; as well as risks, benefits, and costs of participation. Additionally, participants will be told that they could stop participation at any point without negative repercussions. Participants select one of the following options: "Yes, I understand this and want to participate in the PROMOTING MONITORING: A PILOT TEST study" or "No, I do not want to participate in the study." Those who provide consent to participate in the study will proceed to baseline assessment, followed by randomization to either the contingency management (CM) or control (Co) group.

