### ***Outcome Measures***

As shown in Table 4, the primary outcome measures are the number of completed daily self-monitoring surveys and the longest period of sustained adherence to survey completion. It is hypothesized that those in the CM group will complete more daily self-monitoring surveys and have a longer sustained period of daily survey completion compared to controls. The number of completed daily surveys and duration of continuous daily survey completion will be compared between CM and Co groups using independent *t*-tests.

Secondarily, descriptive statistics will be used to summarize CM participants' self-report of the impact of behavioral incentives on adherence. Mean time to complete the daily surveys between CM and Co groups will be compared using an independent *t*-test. Pain experience and

related variables from baseline will be compared to follow up responses for the total sample using paired *t*-tests. The daily survey item responses will be summarized for the overall sample using descriptive statistics. Associations between daily survey and follow-up TFLB for alcohol and prescription opioid use data for the overall sample and each study group will be examined using Spearman's correlations. Descriptive statistics will be used to summarize self-report validity and accuracy of responses. Feasibility and acceptability of CM app implementation will be examined by comparing follow-up acceptability survey ratings for each group using independent *t*-tests.

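### Does the lack of a named analysis set leave the two primary adherence outcomes, and the pilot effect size, open to selective exclusion?

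*Combined protocol and SAP*

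**What the plan says.** Sample Size Justification sizes a two-sided t-test at 32 per group, quotes a detectable d of .711, and adds: "Recruitment of 80 subjects with 80% retention was expected to achieve this effect size". It does not define retention or say which outcomes the 80% applies to.

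Outcome Measures gives the primary analysis: "The number of completed daily surveys and duration of continuous daily survey completion will be compared between CM and Co groups using independent" t-tests. Table 4 defines the second primary outcome as the largest number of consecutive days with a completed survey in the 28-day period. Effect Size Estimation takes the pilot's main product from the same data: "This will be done by using the means and variances of the CM and Co groups on the primary outcome variables".

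On timing, the DynamiCare Rewards App paragraph under Baseline Visit Call says "After randomization, all participants will be added to the DynamiCare Analytics portal" and are then emailed the download link. The All Participants paragraph says "Day 1 of the daily surveys will start the day after the app is downloaded and the account is set up". Under Informed Consent, "participants will be told that they could stop participation at any point without negative repercussions".

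No section names an all-randomised, app-started or completer population. No section excludes anyone after randomisation either. The only non-contact rule, under Baseline Assessment, operates before randomisation.

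**The concern.** Three features together look like an opening for bias. First, the population is unnamed. Second, the sizing removes 20%, which could suggest that only retained people enter the primary t-tests, although app-logged counts need no follow-up visit. Third, the 28-day clock starts at app set-up, so someone randomised who never installs the app has no Day 1.

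A non-completed survey is itself an outcome value here, and only one arm is paid to complete surveys. Leaving out disengaged people would select on the outcome after randomisation. Aim 5 carries the resulting effect size into the design of a larger trial. Low scorers alter both the group means and the SD, so the distortion could go either way. The literature review also describes a daily-diary study with a quarter "of the sample excluded for having <25% of self-reports", which shows that exclusion of low reporters does occur in this field.

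**Working it through.** **1. Reproduce the plan's figure.** Inputs from Sample Size Justification: two-sided alpha .05, 80% power, 32 per group, 80 recruited, 80% retained.

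- Retained: 80 × 0.80 = 64, or 32 per group.
- Power comes from the noncentral t with n1 + n2 − 2 degrees of freedom and noncentrality d × √(n1·n2/(n1+n2)). For 32/32 the multiplier is √16 = 4.
- Detectable d = 0.711; power at d = .711 is 79.9%. As a rough check, (1.96 + 0.84)/4 = 0.70.

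The stated figure is right for 32 per group.

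**2. Analyse everyone instead.** The Randomization paragraph gives 46 CM and 35 Co.

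| Analysed (CM/Co) | Detectable d | Power at d = .711 |
|---|---|---|
| 32/32 | 0.711 | 79.9% |
| 40/40 | 0.634 | 88.1% |
| 46/35 | 0.636 | 87.9% |
| 37/28 (80% of 46/35) | 0.713 | 79.8% |

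At a given d, analysing all 81 gains power relative to the printed sizing.

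**3. Who has a score under the plan's definitions?**

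- *Set up, then stops.* The number completed and the longest run are both defined over the 28-day period. A day without a survey adds nothing to the count and ends a run. Someone who completes days 1 to 5 and then stops scores 5 and 5. No imputation rule is needed.
- *Randomised, never set up.* This person completed no surveys, but the 28-day window has no formal start. The opening of Baseline Visit Call lists verification, randomisation and app set-up as contents of one 5–10 minute call. The Co Group paragraph has controls download the app during that call, and the CM Group paragraph attaches the initial draw to downloading and training during it. The Randomization paragraph assigns those who have finished the call, while the app paragraph sends the link after randomisation. The order is blurred, but either way the gap lies within one live call.

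**4. How much could never-started people matter?** The documents give no rate, so this is an illustration. Assume engaged means of 21 (CM) and 18 (Co) with SD 6, so d = 3/6 = 0.50 among starters, and score never-started people 0. With a fraction q never started in an arm whose starters have mean μ:

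- arm mean = (1 − q)μ
- arm variance = (1 − q)·SD² + q(1 − q)·μ²

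For two never-started in CM, q = 2/46. The mean is 20.09 and the variance 52.8. The pooled SD is √((45 × 52.8 + 34 × 36)/79) = 6.75, so d = 2.09/6.75 = 0.31.

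| Never started (CM/Co) | d, all randomised | Next trial, per group |
|---|---|---|
| 0/0 | 0.50 | 64 |
| 1/1 | 0.46 | 76 |
| 0/2 | 0.62 | 43 |
| 2/0 | 0.31 | 166 |

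Under two other assumed settings (22 vs 19.5 with SD 5; 20 vs 16.5 with SD 7), the 1/1, 0/2 and 2/0 rows run over 0.44–0.47, 0.60–0.63 and 0.26–0.35.

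**5. Put that beside sampling error.** For d = 0.50 at 46/35, SE ≈ √(1/46 + 1/35 + 0.50²/(2 × 81)) = 0.228. The approximate 95% interval is 0.50 ± 1.96 × 0.228, or 0.05 to 0.95, wider than the whole 0.26–0.63 range.

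**The case for a change.** The strongest argument for a change is that effect-size estimation is the pilot's declared purpose, so the population behind it should not be left to inference. Two people can shift d noticeably, and a 20% deduction within the sizing of the very test used for the primary outcomes hints at a completer analysis. The remedy would be a few sentences, applied from app logs and the randomisation list. Bias is also not excused by wide sampling error.

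Part of this stands. No sentence names the population or defines retention, and an explicit statement would read better. The rest is weaker. The deduction fits the follow-up survey at least as well, since t-tests on acceptability ratings are also planned there. The cited diary study's exclusion rule appears in the literature review as evidence that adherence was poor, and nothing in the Data Analysis Plan adopts it. The largest swings come from borrowing that rule, applying it to 16 of the 81, and giving them 0 to 6 surveys each. The all-randomised d then runs from about 0.25 to 0.82 depending on the assumed split between arms. That combination is not in the plan. Moving app installation ahead of allocation would alter trial procedure for a problem of undocumented frequency, with no gain shown.

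**Conclusion.** No change follows. This is missing detail that a competent analyst would fill in one way: compare the groups as randomised, with uncompleted days simply not counted. That reading rests on three points in the text: the groups are defined by random assignment, the outcome definitions already score anyone who stops, and no post-randomisation exclusion exists.

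The sizing causes no harm. Its 0.711 is correct for 32 per group, and the figure is about 0.64 if all 80 or 81 are analysed.

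The residual uncertainty is anyone randomised but never set up. Zero is the natural score for such a person, and a participant count by arm would show whether any exist. Two of them in one arm would matter (d of 0.26–0.63 against 0.50 under the assumed settings), but the means, SDs and splits are all assumptions. Because set-up is part of the randomisation call, the number is expected to be small. The conclusion would differ if the plan restricted the primary analysis to retained or set-up participants; it does not.
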